### **3.6.11 Patient Reported Outcomes**

#### **3.6.11.1 Asthma Control Questionnaire**

The ACQ (see sample in Appendix 4) will be completed at visits specified in the study schedule. The ACQ is a 6-item subject reported questionnaire to assess the recall over the prior week with 6 items addressing night-time waking, symptoms on waking, activity limitation, shortness of breath, wheeze, and rescue short-acting beta agonist use (Juniper et al, Oct 1999). Questions are rated on a 7-point Likert scale from 0 (no impairment) to 6 (maximum impairment) where scores of  $\leq 0.75$  indicate well-controlled asthma and scores  $>1.5$  indicate uncontrolled asthma (Juniper et al; 2006). Individual changes of 0.5 are considered to be clinically meaningful (Juniper et al, 2005)

Although not required by protocol, it is preferable if the ACQ is the first assessment completed during the study visit.

### **3.6.11.2 Asthma Quality of Life Questionnaire (Standardized Version)**

The AQLQ(S) (see sample in [Appendix 5](#)), will be completed at visits specified in the study schedule. The AQLQ(S) is a 32-item questionnaire that measures the functional impairments experienced by adults 17 years and older ([Juniper et al, May 1999](#)). It has 4 domains (symptoms, activity limitations, emotional function, and environmental stimuli). Subjects are asked to recall their experiences during the previous 2 weeks and to score each of the 32 questions on a 7-point scale from 7 = no impairment to 1 = severe impairment. The overall score is calculated as the mean response to all questions. The 4 domain scores (symptoms, activity limitations, emotional function and environmental stimuli) are the means of the responses to the questions in each of the domains. Individual improvement for both the overall and individual domain scores of 0.5 have been identified as the minimally important difference, with changes >1.5 to be large meaningful differences ([Juniper et al, 1994](#)).

Although not required by protocol, it is preferable if the AQLQ(S) is completed after the ACQ and prior to other assessments.

### **3.6.11.3 Healthcare Resource Utilization and Economics**

Healthcare resource use will be summarized from information on asthma exacerbations, and asthma related medications. Absolute number and proportion of healthcare resource utilization by resource type will be reported.

## **3.7 Completion of Study and Loss to Follow-up**

Subjects will be considered to have completed the study if they were followed up through Study Day 168. It should be specified on the source document whether or not the subject completed the study follow-up procedures through Study Day 168.

Subjects will be considered lost-to-follow-up only if no contact has been established by the time the study is completed such that there is insufficient information to determine the subject's status at Study Day 168. Investigators should document attempts to re-establish contact with missing subjects throughout the study period. If contact with a missing subject is re-established, follow-up should resume according to the protocol.

## **4 Safety Assessment**

### **4.1 Adverse Events**

#### **4.1.1 Definition of Adverse Events**

As defined by the ICH Guideline for Good Clinical Practice (CPMP/ICH/135/95), an adverse event (AE) is:

Any untoward medical occurrence in a subject or clinical investigations subject administered a pharmaceutical product and which does not necessarily have to have a causal relationship with this treatment.

An AE can therefore be any unfavorable and unintended sign (including an abnormal laboratory finding), symptom, or disease temporally associated with the use of a medicinal product, whether or not considered related to the medicinal product.

An AE includes but is not limited to:

- Any clinically significant worsening of a pre-existing condition;
- An AE occurring from overdose (ie, a dosage higher than that prescribed by a healthcare professional for clinical reasons, or a dosage higher than that described on the marketed product label) of an investigational or marketed product, whether accidental or intentional;
- An AE occurring from abuse (eg, use for nonclinical reasons) of an investigational or marketed product;
- An event related to a medical procedure or associated with the discontinuation of the previous use of an investigational or marketed product required by protocol (protocol-related AE).

#### **4.1.2 Study Reporting Period for Adverse Events**

All adverse events that occur after a subject has received the investigational product through Study Day 84 must be reported by the investigator.

Any new sign or symptom, disease, or other untoward medical event that occurs after the subject signs the informed consent form but before the subject has received investigational product, and which may possibly be causally related to the protocol (ie, results from a

required procedure or from withdrawal of prior medication), must be reported by the investigator as an adverse event in the same way as adverse events that occur after the subject receives investigational product.

### **4.1.3 Recording of Adverse Events**

All AEs will be recorded using the collection instrument provided. Adverse events will be reported using a recognized medical term or diagnosis that accurately reflects the event. AEs will be assessed by the investigator for severity, relationship to the investigational product, possible etiologies and whether the event meets criteria as a SAE and therefore requires immediate notification of the sponsor. See Section 4.2.1 for the definition of SAEs, and Section 4.3 and Section 4.4 for guidelines for assessment of severity and relationship, respectively. If the event has not resolved at the end of the study reporting period it will be documented as ongoing. If an AE evolves into a condition which becomes “serious” it will be reported on the SERIOUS ADVERSE EVENT (SAE) REPORT FORM.

## **4.2 Serious Adverse Events**

### **4.2.1 Definition of Serious Adverse Events**

A Serious Adverse Event (SAE) is any AE that:

- Results in death;
- Is immediately life-threatening

This term refers to an event in which the subject was at risk of death at the time of the event; it does not refer to an event that hypothetically might have caused death if it were more severe.

- Requires inpatient hospitalization or prolongation of existing hospitalization.

In general, hospitalization signifies that the subject has been detained (usually involving at least an overnight stay) at the hospital or emergency ward for observation and/or treatment that would not have been appropriate in an outpatient setting. Complications that occur during hospitalization are AEs. If a complication prolongs hospitalization or fulfills any other serious criteria, the event is serious. When in doubt as to whether “hospitalization” occurred or was necessary, the AE should be

considered serious. Hospitalization for elective treatment of a pre-existing condition that did not worsen from baseline is not considered an AE.

- Results in persistent or significant disability/incapacity.

The term disability means a substantial disruption of a person's ability to conduct normal life functions. This definition is not intended to include experiences of relatively minor medical significance such as uncomplicated headache, nausea, vomiting, diarrhea, influenza, and accidental trauma (eg, sprained ankle) which may interfere or prevent everyday life functions but do not constitute a substantial disruption.

- Is a congenital anomaly/birth defect in offspring of the subject.

A pregnancy should be reported to MedImmune Product Safety as an immediately reportable event (IRE). A pregnancy should be followed for outcome and the health status of the mother and the child. If the child is born with any congenital anomaly of birth defect, this should be reported to Product Safety as a SAE.

- Is an important medical event that may jeopardize the subject or may require medical intervention to prevent one of the outcomes listed above.

Medical or scientific judgment should be exercised in deciding whether expedited reporting is appropriate in this situation. Examples of medically important events are intensive treatment in an emergency room or at home for allergic bronchospasm, blood dyscrasias, or convulsions that do not result in hospitalizations; or development of drug dependency or drug abuse.

A serious event related to a medical procedure required by protocol prior to dosing of the study medication should also be reported to Product Safety as an SAE (protocol-related SAE).

#### **4.2.2 Study Reporting Period for Serious Adverse Events**

The reporting period for SAEs is the period immediately following the time that written informed consent is obtained through Study Day 84. After the initial SAE report the investigator is required to follow each subject proactively and provide further information on the subject's condition to MedImmune Product Safety.

All SAEs should be followed up to resolution by the investigator, even if this extends beyond the study reporting period. Resolution of an SAE is defined as the return to baseline status or stabilization of the condition with the expectation that it will remain chronic.

At any time after completion of the study, if an investigator or qualified designee becomes aware of an SAE that is suspected by the investigator or qualified designee to be related to investigational product, the event should be reported to MedImmune Product Safety.

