#### **1.4 Clinical Experience with MEDI-563**

MEDI-563 is currently being investigated in two Phase 1 studies, MI-CP158 and MI-CP166, and one Phase 2 study, MI-CP197. MI-CP158 is an open-label, dose-escalation study to evaluate the safety and tolerability of a single IV infusion in adults with mild asthma. MI-CP166 is a double-blind, placebo-controlled study to evaluate the safety, tolerability and effects of MEDI-563, on airway eosinophils in adults with asthma. MI-CP197 is a randomized, double-blind, placebo-controlled, dose-escalation study to evaluate the safety and tolerability of multiple-dose SC administration of MEDI-563.

Accrual has been completed in MI-CP158. In this study, MEDI-563 was administered as a single IV infusion of 0.0003, 0.003, 0.03, 0.1, 0.3, 1.0, or 3.0 mg/kg. A total of 44 subjects received MEDI-563 in this study. Results showed that a single IV dose of MEDI-563, as low as 0.03 mg/kg, depleted eosinophils to below the level of detection for at least 8 weeks. At the 3.0 mg/kg dose, 2 of 4 subjects experienced a cluster of adverse events (AEs) following administration of MEDI-563. One subject experienced nausea, lightheadedness, fever, chills, and headache 7 hours after the infusion, and one subject experienced headache, fever, chills, flushing, and fatigue after the infusion. A third subject had a headache after the infusion but no cluster of AEs. It was found that the site did not use a filter during infusion and the infusion time was short. No additional events were seen after a filter was required for infusion and a minimum infusion rate of at least 30 minutes was required. In the high dose groups (1.0 and 3.0 mg/kg) the eosinopenia lasted up to 12 to 16 weeks and conversely, in the low dose groups (0.003 and 0.0003 mg/kg) eosinopenia lasted an average of 2 weeks and 1 to

2 days, respectively demonstrating that the effects of MEDI-563 are dose-dependent. The pharmacokinetics (PK) of MEDI-563 was linear with dose and typical for a human IgG.

Additional clinical information can be obtained from the Investigator Brochure.

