## 2.3 Overview

### Study Design

This is a Phase 2, randomized, double-blind, placebo-controlled study to evaluate the effect of two IV dose regimens of MEDI-563 (0.3 and 1.0 mg/kg) on the proportion of asthma exacerbations (relapse and de novo) at Week 12 in adult subjects who required an urgent healthcare visit for treatment of an acute asthma exacerbation. Approximately 15 to 20 sites in North America will participate in this study. At least 108 evaluable subjects will be randomized using a 2-step stratified randomization procedure. The first step (Step 1) will randomize subjects in a 1:1 ratio to Treatment Arms I or II, and the second step (Step 2) will randomize subjects in each treatment group in a 2:1 ratio to receive a single IV dose of MEDI 563 or placebo as described in [Figure 2.3-1](#). Prior to being randomized into a treatment arm subjects will be stratified by baseline eosinophil levels in peripheral blood ( $>450$  eosinophils/mm^3 vs.  $\leq 450$  eosinophils/mm^3). However, no subjects will be excluded based on screening eosinophil levels in peripheral blood.

Subjects are considered evaluable if they receive the investigational product, and are followed according to the protocol through Study Day 42. Nonevaluable subjects will be replaced and the new subject will receive the same treatment assignment as the replaced subject.

Investigational product (MEDI-563 or placebo) will be administered on Study Day 0 (within 7 days of meeting eligibility criteria). The subject's FEV1 must be  $\geq 30\%$  predicted prior to administration of the investigational product.

Investigational product will be administered as a single IV infusion over a period of at least 30 minutes through a 0.22 µm protein-sparing/low in-line filter, which will be supplied by the sponsor. If the subject weighs  $\geq 130$  kg, the infusion time will be increased to at least 60 minutes. Subjects will be followed for a total of 24 weeks after administration of the investigational product.

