### **3.4.5 Concomitant Medications**

Use of concomitant medications, other than those provided per protocol (systemic prednisone [ $\geq$  40 mg/day] for 7 days, inhaled rescue albuterol for the entire study period, and ICS as prescribed, see Section 3.4.2) from Study Day 0 through Study Day 84 are discouraged. However, subjects may receive medications to treat AEs as deemed necessary by the investigator or the subject's physician.

All concomitant medications given to the subject from screening through Study Day 84, including those given in the urgent healthcare setting or in the EMS to treat the initial acute asthma exacerbation will be recorded on the source document. The following medications are considered exclusionary, and the sponsor must be notified if a subject receives any of these through Study Day 84.

- 1) Immunosuppressive medication (corticosteroids are permitted)
- 2) Investigational agents
- 3) Xolair®

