**Study Day 112: Follow-up Phone Call ( $\pm$  3 days)**

- 1) Assess for asthma exacerbation

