### **3.6.9 Concomitant Medications**

Study subjects will be given systemic prednisone ( $\geq$  40 mg/day for 7 days) and inhaled rescue albuterol for the duration of the study (1 canister per month). In addition, subjects not currently taking an ICS will be given a prescription for fluticasone propionate, dose to be determined by the investigator or designee based upon severity of symptoms. Subjects currently taking an ICS will be advised to continue using as prescribed. Subjects will be instructed on medication use and these will be recorded on the source document and in the validated data collection instrument provided.

Use of concomitant controller and rescue medication will be collected daily by the subject from screening through Study Day 84. Instructions will be provided to each enrolled subject at screening/Study Day 0. At each follow up visit, subjects will be assessed specifically for the need to add ICS and this will be recorded.

All other concomitant medications the subject takes, including vitamins and supplements from screening through study termination will be recorded.

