## **5.5 Secondary Endpoints**

### **5.5.1 Safety Assessment**

The safety of MEDI-563 in this subject population is a secondary objective of this study. Adverse events will be summarized categorically by system organ class, preferred term, severity, and relationship to investigational product through Study Day 84. Serious adverse events will be assessed through Study Day 84. Laboratory abnormalities, for tests such as serum CRP, ECP, and IL-6 levels will be evaluated in the MEDI-563 and placebo groups as changes from baseline.

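### AE and SAE reporting ends at Study Day 84 while telephone follow-up runs to Day 168: Days 85–168 fall between two SAE rules, and up to 28 days of possible eosinophil depletion have no solicited safety data

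*Protocol*

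**What the plan says.** **Safety window.** Section 4.1.2: "All adverse events that occur after a subject has received the investigational product through Study Day 84 must be reported by the investigator". Section 4.2.2: "The reporting period for SAEs is the period immediately following the time that written informed consent is obtained through Study Day 84". The analysis follows suit in Section 5.5.1: "Serious adverse events will be assessed through Study Day 84". The same limit appears in the abstract, in Section 4.2.4 (notifying the IRB or IEC), in Section 4.6 (medical monitor review) and in Section 7.2. Table 3.5-1 has no AE, SAE, hematology, chemistry, PK or antibody entry after Day 84.

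**Follow-up window.** The abstract and Section 2.3 state: "Subjects will be followed for a total of 24 weeks after administration of the investigational product". Section 3.7 defines completion as follow-up through Day 168. The visit lists for the Day 112, 140 and 168 calls each hold one item: "Assess for asthma exacerbation".

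**Duration of effect.** Section 1.4, on the single-dose Phase 1 study: "In the high dose groups (1.0 and 3.0 mg/kg) the eosinopenia lasted up to 12 to 16 weeks". The present trial uses 0.3 and 1.0 mg/kg.

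**Late SAEs.** The last paragraph of Section 4.2.2 asks for an SAE to be reported at any time after the study is completed, if the site learns of it and suspects a relationship to investigational product. Section 4.2.3 (notice to the sponsor within 24 hours) and Section 7.1 (report to sponsor and IRB/IEC) apply regardless of relationship and give no end date.

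**Concomitant medication.** Section 3.4.5 covers "All concomitant medications given to the subject from screening through Study Day 84", and Table 3.5-1 agrees. Section 3.6.9 says: "All other concomitant medications the subject takes, including vitamins and supplements from screening through study termination will be recorded".

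**The concern.** Safety is the first secondary objective. The safety window closes halfway through follow-up, at a point the protocol's own Phase 1 summary places inside or at the end of the period of eosinophil depletion for one of the two doses. The site still speaks to each subject three more times but is not told to ask about serious events.

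The reporting rules after Day 84 also do not fit together. Two sites that learn of the same event on Day 100 could act differently, one following the Day 84 limit and the other the undated duty in Section 4.2.3 or 7.1. Events that reach the sponsor this way depend on chance and on local reading of the text, so they give no sound comparison between arms.

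**Working it through.** **1. The windows in days.**
- AE and SAE reporting: Day 84 = 84/7 = 12 weeks.
- Follow-up: 24 weeks × 7 = 168 days.
- Without solicited AEs or SAEs: 168 − 84 = 84 days, and 84/168 = 50% of post-dose follow-up.

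**2. Overlap with reported depletion.** Section 1.4 gives 12 to 16 weeks as an upper range for the two high-dose groups together.
- At 16 weeks: 16 × 7 = 112; 112 − 84 = 28 days uncovered; 28/112 = 25% of a 16-week depletion.
- At 12 weeks: 12 × 7 = 84; 0 days uncovered, but nothing is collected during recovery.
- The gap is therefore 0 to 28 days, in some subjects of the 1.0 mg/kg arm. For 0.3 mg/kg, Section 1.4 gives no upper duration, only depletion for at least 8 weeks at doses down to 0.03 mg/kg.

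**3. Which rule applies to an SAE, by day.**

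| Time of event | Main rule, 4.2.2 | Late rule, 4.2.2 | 4.2.3 and 7.1 |
|---|---|---|---|
| Consent to Day 84 | applies | not needed | apply |
| Day 85 to Day 168 | ended | not yet begun | no end date stated |
| After completion | ended | suspected-related only, if the site learns of it | no end date stated |

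If completion means the end of the whole trial rather than of one subject's follow-up, the late rule begins no earlier than Day 168 for that subject, and the hole is at least as long.

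**4. What is still captured.** Section 3.6.10.1 collects onset, healthcare visit, treatment and resolution for every exacerbation to Day 168. Seriousness and causality are not among the listed items.

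**5. Possible size, as an illustration only.** The protocol's quantitative safety figures are in Tables 5.2.1-1 and 5.2.1-2. The first gives P(at least one event) = 1 − (1 − p)^n. At p = 1.0%: 1 − 0.99^36 = 30.4% and 1 − 0.99^72 = 51.5%, as printed; all 14 rows reproduce. Now assume, which the protocol does not state, a constant hazard with risk r by Week 12. The risk by week w is then 1 − (1 − r)^(w/12). For r = 1.0% this is 1.33% by Week 16 and 1.99% by Week 24.

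| r by Week 12 | n | to Week 12 | to Week 16 | to Week 24 |
|---|---|---|---|---|
| 0.5% | 36 | 16.5% | 21.4% | 30.3% |
| 1.0% | 36 | 30.4% | 38.3% | 51.5% |
| 2.0% | 36 | 51.7% | 62.1% | 76.7% |
| 0.5% | 72 | 30.3% | 38.2% | 51.4% |
| 1.0% | 72 | 51.5% | 61.9% | 76.5% |
| 2.0% | 72 | 76.7% | 85.6% | 94.5% |

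After a single dose the hazard of a drug-related event may well fall over time, and the gain would then be smaller.

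**The case against.** **Day 84 is deliberate and uniform.** Every section that dates the safety window gives the same day. As context, Appendix 6 records that the later calls were meant for exacerbations only, and that 84 days was chosen as more than 5 half-lives. This stands: the limit is a design choice and not a slip. The half-life reason, however, concerns exposure rather than duration of depletion, and was given when the study ended at Day 84.

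**The depletion figure is pooled.** A reader might infer that depletion at 1.0 mg/kg is known to outlast safety collection. Section 1.4 does not support that. It combines 1.0 with 3.0 mg/kg, the latter is not used here, and the 16-week end may come from it. Hence a range that starts at 0 days.

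**Late serious events are not invisible.** A reader might infer that a hospitalized exacerbation on Day 120 would be lost or would not be an SAE. It would be recorded as an exacerbation, and it meets the definition in Section 4.2.1; only the reporting window leaves it out. Section 3.5 also tells subjects to call about abnormalities between study visits and has outside medical records obtained, and the safety committee reviews data throughout the study. These narrow the loss without replacing a direct question. The Section 3.5 instruction concerns intervals between visits, and the protocol labels Day 84 the last study visit.

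**The concomitant-medication mismatch is a different matter.** It does not bear on SAE reporting. A reader might infer that Week 24 results could not be separated from use of exclusionary drugs. Section 3.6.9, taken literally, would record such drugs to study termination, and the Week 24 comparison is exploratory. What remains is that Section 3.4.5 and Table 3.5-1 disagree with Section 3.6.9, and no later call asks about medication.

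**Conclusion.** The point holds as a design weakness with one real gap in the rules. Half of post-dose follow-up (84 of 168 days) has no solicited AE or SAE data. Within it lie 0 to 28 days of possible depletion in some 1.0 mg/kg subjects, resting on the pooled range in Section 1.4, and any recovery after that.

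The 50% is a share of time. It should not be read as the share of safety information lost, which depends on an unknown hazard. Because exacerbations are followed to Day 168, the loss is mainly of other serious events and of SAE classification.

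The more definite defect is in Section 4.2.2. Taken literally, even a suspected-related SAE on Days 85 to 168 is covered by neither of its rules, while Sections 4.2.3 and 7.1 point the other way. The remedy uses contacts already scheduled, so it is worth making even though the size of the gain cannot be fixed from the protocol. The concomitant-medication inconsistency is separate and minor.

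**What to change.** 1. Add a question on SAEs, and on AEs the investigator considers related, to the Day 112, 140 and 168 calls.
2. Change the reporting period to Day 168 everywhere it is stated: the abstract, Table 3.5-1, the three visit lists, and Sections 4.1.2 (related AEs only after Day 84), 4.2.2, 4.2.4, 4.6, 5.5.1 and 7.2. Also update the description of the calls in Section 2.3. Changing only some of these would create contradictions that do not now exist.
3. With Section 4.2.2 extended to Day 168, its late rule follows on without a hole. Check that Sections 4.2.3 and 7.1 refer to the same period.
4. Tabulate Days 0–84 and 85–168 separately, so that the safety summary at the second interim analysis, after all Day 84 evaluations, keeps its present scope.
5. Separately, reconcile Section 3.4.5 and Table 3.5-1 with Section 3.6.9 on when recording of medication ends, and record asthma controllers and the listed exclusionary drugs at the same calls.

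Cost: a protocol amendment, a CRF page and some extra SAE processing, with no new visits or procedures. Calls will not supply eosinophil counts, so the later data will show events but not whether the subject was still depleted.
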